### **Total population:**

Any patient who withdraws from the randomised phase of the study will be included in the safety analysis (AEs and laboratory parameters). Data for all patients will be listed, and a list of withdrawn patients, with all reasons for withdrawal, will be given.

Total population also includes data for those patients who, after having consented to participate, underwent screening examinations required for inclusion into the study but who, because a criterion for exclusion was met or for other reasons, were not included in the study.

## 12.7 Safety Analysis

Demographic information, medical history and physical examination data will be listed for each patient and summarised descriptively.

All AEs recorded during the study will be coded to system organ class and preferred terms using the current version of the Medical Dictionary for Regulatory Activities (MedDRA). Treatment-

emergent AEs will be tabulated and summarised by treatment, relationship to treatment, seriousness and severity. Non-treatment emergent AEs will be listed separately.

Clinical laboratory values (haematology, biochemistry, and coagulation) will be listed for each patient by treatment and day. Values outside the laboratory normal ranges will be listed separately with associated comments as to their clinical significance, with potentially clinically significant abnormalities highlighted and summarised by treatment. Clinical laboratory values obtained prior to dosing will be defined as baseline values.

Individual values of vital signs will be listed and summarised descriptively for each treatment and day.

ECG assessments will be listed for each patient with all associated comments and summarised by treatment and day.

Concomitant medications (if any), categorised by medication group and subgroup according to the latest version of the World Health Organisation drug dictionary (WHODD), will be listed and summarised by treatment.

In general, appropriate descriptive statistics, according to the nature of the variable, will be applied. Categorical variables will be presented using counts and percentage, whilst continuous variables will be presented using mean, standard deviation, median, minimum, maximum, coefficient of variation and number of patients.

## 12.8 Statistical Analysis Plan

In addition to the summarised analysis outlined below, a separate document, SAP for DS102A-05-AH1, will detail all analysis to be performed.

### 12.8.1 Pharmacokinetic Analysis

PK will be analysed using the following parameters:

#### Pilot Phase:

- $C_{\max}$  – maximum observed concentration
- $T_{\max}$  - time of maximum observed concentration
- $AUC_t$  – Area under the concentration-time curve to time  $t$
- $AUC_{\text{tau}}$  - Area under the concentration-time curve to the end of the dosage interval
- $AUC_{\infty}$  - Area under the concentration-time curve extrapolated to infinite time
- %Extrap – Percentage of  $AUC_{\infty}$  obtained by extrapolation
- $K_{\text{el}}$  – Apparent first-order terminal elimination rate constant
- $T_{1/2}$  – Apparent first-order terminal elimination half-life

- $F_{lucp}$  – Fluctuation at pharmacokinetic steady-state
- $R_{ac}$  – Accumulation ratio at pharmacokinetic steady-state
- $T_{ss}$  – Time to achieve pharmacokinetic steady-state

**Double-Blind Phase:**

- $R_{ac}$  – Accumulation ratio at pharmacokinetic steady-state
- $T_{ss}$  – Time to achieve pharmacokinetic steady-state

### **12.8.2 Primary Variables**

The primary efficacy variable will be change in MELD score from baseline to Day 28. This change in MELD score and its difference between treatment groups will be estimated using a General Linear Repeated Measures Model with treatment arm, baseline MELD value, visit and treatment arm by visit interaction as factors. The primary analysis will be based on the FAS and repeated for the PPS as a supportive analysis.

### **12.8.3 Secondary variables**

The secondary and exploratory efficacy variables will be summarised with descriptive statistics per treatment group and visit. The change from baseline to Day 28 (and other visits) for the active treatment group will be compared against placebo either via logistic regression or analysis of covariance taking the baseline level as covariate into account. Survival time will be analysed using the Cox Proportional Hazards model including treatment group and MELD score at baseline as covariate. The 5% level of significance will be used for all treatment comparisons of secondary and exploratory endpoints without adjustment for multiplicity.

A new secondary efficacy variable will be a 5-level ordinal variable combining change of MELD score from baseline, premature treatment terminations and mortality as follows; each patient will be allocated to the first level that occurs

- level 1: death within 28 days,
- level 2: death within 90 days,
- level 3: early treatment termination because of safety issues or lack of efficacy,
- level 4: no improvement in Meld Score at day 28 compared to baseline,
- level 5: improvement in Meld Score at day 28 compared to baseline

Patients with lost to follow up within 28 days will be allocated to level 4 or 5 according to their imputed result at day 28 based on the model in 12.9.2 as for these patients the MAR assumption seems appropriate.

This ordinal variable will be analysed using ordinal logistic regression with MELD score as baseline covariate ( $\alpha=0.05$  two-sided). An odds ratio including 95%-confidence limits will be calculated as measure of effect size for this variable.

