### 5.3 Exploratory Endpoints

- Survival at day 7, 14, 21, 28 and 90 using Kaplan-Meier Plot
- Change in GT from baseline to Day 7, 14, 21 and 28
- Change in ALT from baseline to Day 7, 14, 21 and 28.
- Change in Child Pugh score from baseline to Day 7, 14, 21 and 28
- Change in APACHE-II score from baseline to Day 7, 14 and 28
- Change in Lille score from baseline to Day 7, 14 and 28

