## 9 ASSESSMENTS

### 9.1 Efficacy Assessments

#### 9.1.1 Model for End-Stage Liver Disease

The model for end-stage liver disease (MELD) is employed in the evaluation of hepatic function and the assessment of prognosis. MELD is calculated based on variables including the international normalised ratio (INR), serum creatinine, and serum bilirubin.

A MELD score  $\geq 18$  (within 24 hours of presentation) is considered a good predictor of 90 day mortality in patients with AH.

MELD will be assessed at Visit 1/Screening, Visit 2/Baseline, Visit 3/Day 3, Visit 4/Day 5, Visit 5/Day 7, Visit 6/Day 14, Visit 7/Day 21, Visit 8/Day 28/Early Termination and Visit 9/Day 90/Follow up.

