#### 9.1.9 Acute Physiologic and Chronic Health Evaluation II

The acute physiologic and chronic health evaluation (APACHE) II score (see appendix 15.3) will assess patients for the presence of multiple organ dysfunction and predict mortality by generating a point score ranging from 0 to 71 based on twelve physiologic variables, age and underlying health.

APACHE II will be assessed at Visit 2/Baseline, Visit 3/Day 3, Visit 4/Day 5, Visit 5/Day 7, Visit 6/Day 14, Visit 7/Day 21, Visit 8/Day 28/Early Termination and Visit 9/Day 90/Follow up.

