#### 9.1.10 Lille Score

The Lille score is a composite score which predicts mortality in patients with AH who are not responding to steroid therapy. It is based on age, albumin, bilirubin (initial), bilirubin (day 7), creatinine and PT; a score of >0.45 identifies 75% of deaths, a score of >0.45 predicts a 6-month survival of 25%, and a score of <0.45 predicts survival of 85%.

Lille score will be assessed at Visit 2/Baseline, Visit 3/Day 3, Visit 4/Day 5, Visit 5/Day 7, Visit 6/Day 14, Visit 7/Day 21, Visit 8/Day 28/Early Termination and Visit 9/Day 90/Follow up.

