6.8 Background and Demographic Characteristics

6.8.1 Demography

Demographic characteristics (age, sex, ethnic origin and race), body measurements (height, weight, body mass index (BMI)), alcoholic hepatitis duration, average weekly consumption of alcohol (units per week) and the presence of a history of alcohol abuse for > 6 months (Yes/No) will be summarised by treatment group and overall.

Age at informed consent is captured on the electronic case report form (eCRF).

BMI is calculated as (weight (kg)/height (m)²).

Date of alcoholic hepatitis diagnosis will be recorded. Alcoholic hepatitis duration will be calculated in years as [date of informed consent - date of alcoholic hepatitis

diagnosis+1]/365. Dates will be imputed according to this rule: if the day is missing, day will be imputed as 1st day of the month, if the month is missing, month will be imputed as 1st month of the year.

All patient demographic data including informed consent, AH diagnosis and substance use data will be listed.

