6.13 Exploratory Endpoints

6.13.1 Survival at day 7, 14, 21, 28 and 90

Survival time will be derived as:

(Death date/last date patient known to be alive – date of randomisation + 1).

Survival time will be analysed with a Cox proportional hazards model including covariates for treatment group and baseline MELD score. Tied observations will be

handled using the Breslow-Henshaw method. The assumption of proportional hazards will be assessed visually using the log-log plot.

Estimates for the hazard ratio (DS102:Placebo), associated 95% CI and p-values will be presented.

Estimates of survival rate and associated 95% CI at days 7, 14, 21, 28 and 90 will be presented for each treatment group.

Kaplan-Meier plot of the probability of survival against time (days) will be presented for each treatment group.

6.13.2 Change in GT from baseline to day 7, 14, 21 and 28

Gamma glutamyl transferase is a liver enzyme indicative of liver dysfunction and alcohol intake.

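### The Cox survival model adjusts for baseline MELD alone; prespecifying age as a second covariate would be a near-free improvement to an exploratory analysis that is already valid.

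*Protocol*

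**What the plan says.** Protocol 12.8.3: "Survival time will be analysed using the Cox Proportional Hazards model including treatment group and MELD score at baseline as covariate". SAP 6.13.1 agrees: "Survival time will be analysed with a Cox proportional hazards model including covariates for treatment group and baseline MELD score". The SAP reports the hazard ratio with a 95% CI and p-value. Protocol 12.8.3 tests at 5% without multiplicity adjustment. Neither document plans an age-adjusted or age-stratified survival analysis, even as a sensitivity analysis.

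Survival is listed in Protocol 5.3 as an exploratory endpoint: "Survival at day 7, 14, 21, 28 and 90 using Kaplan-Meier Plot". No event count, hazard ratio or power is given for it.

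On age and its role:
- **Lille (Protocol 9.1.10)**, described as predicting mortality: "It is based on age, albumin, bilirubin (initial), bilirubin (day 7), creatinine and PT".
- **APACHE II (Protocol 9.1.9)** is used to "predict mortality by generating a point score ranging from 0 to 71 based on twelve physiologic variables, age and underlying health". Appendix 3 gives age 0 to 6 points.
- **MELD (Protocol 9.1.1)**: "MELD is calculated based on variables including the international normalised ratio (INR), serum creatinine, and serum bilirubin". Age is not listed.
- **Data**: SAP 6.8.1 says that age at consent is captured on the eCRF and summarised by treatment group.
- **Randomisation (Protocol 12.2)** is in permuted blocks stratified by site only.

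**The concern.** The trial's own mortality scores treat age as prognostic, yet the only covariate in the survival model does not carry it, and the randomisation does nothing to balance it. Two consequences follow if age predicts death beyond MELD. First, a chance age difference between the arms moves the estimated hazard ratio in the one trial that is run, and the planned model cannot correct for it. Second, leaving a prognostic factor out of a Cox model pulls the estimate towards no effect and costs some power, even when age is balanced.

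Timing is the practical issue. If the demography table shows an age imbalance after unblinding, any age-adjusted analysis will be post hoc and open to challenge.

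**Working it through.** **The plan's own figure.** Protocol 12.3 gives 55 per group for d = 0.54, two-sided alpha 0.05 and 80% power. The noncentral-t calculation gives power 0.8014 at n = 55, as stated, and all 11 rows of the table reproduce. This concerns MELD change, so it says nothing about survival.

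**Inputs from the documents.** 60 per arm, 1:1 (Protocol 12.3, 12.2); two-sided 5%; follow-up to Day 90.

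**Assumptions.** The documents give no age effect, so age hazard ratios of 1.0 to 2.0 per SD are shown. Protocol 1.1 puts mortality above 30% without a time horizon; 30% and 40% at Day 90 in the placebo arm are used here. Age is taken as independent of MELD, MELD as having a hazard ratio of 1.8 per SD, survival as exponential, and the treatment hazard ratio as 0.5 unless stated.

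**Chance imbalance.** The SD of the between-arm difference in mean age, in SD units, is sqrt(2/60) = 0.183. A 1-in-20 difference is 1.96 × 0.183 = 0.36. The multiplier on the MELD-only hazard ratio (or its inverse, depending on direction) is approximately (age HR per SD)^difference:

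| Age HR per SD | One SE (0.183) | 1 in 20 (0.36) |
|---|---|---|
| 1.2 | 1.03 | 1.07 |
| 1.5 | 1.08 | 1.16 |
| 2.0 | 1.14 | 1.28 |

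Simulation with a true treatment hazard ratio of 1, 30% mortality and the difference fixed at 0.36 SD (2,000 trials each) agrees. The MELD-only hazard ratio was 1.06, 1.15 and 1.27. With age added it was 0.99, 1.00 and 1.02. Rejection rates given that imbalance were 4.6%, 6.4% and 9.5% without age, and 4.8%, 5.0% and 5.4% with it.

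For scale, with 36 deaths (30% of 120) the SE of the log hazard ratio is about 2/sqrt(36) = 0.33. The confidence limits therefore lie a factor of exp(1.96 × 0.33) = 1.9 either side of the estimate.

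**Type I error over all randomisations.** Without age it was 5.4%, 4.8% and 4.7% for age hazard ratios of 1.2, 1.5 and 2.0; with age, 6.0%, 5.1% and 5.0%. Both models hold the 5% level within simulation error.

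**Power** (treatment HR 0.5, 3,000 trials each, both models fitted to the same data):

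| Placebo mortality | Age HR per SD | Mean deaths | MELD only | MELD + age | Gain (points) |
|---|---|---|---|---|---|
| 30% | 1.2 | 28.1 | 41.2% | 41.5% | 0.3 |
| 30% | 1.5 | 28.3 | 39.4% | 42.1% | 2.7 |
| 30% | 2.0 | 28.5 | 37.0% | 41.3% | 4.3 |
| 40% | 1.2 | 38.1 | 53.6% | 54.1% | 0.5 |
| 40% | 1.5 | 38.2 | 51.4% | 53.8% | 2.4 |
| 40% | 2.0 | 39.0 | 46.0% | 53.8% | 7.8 |

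Further runs at 60 per arm, with 20% to 40% mortality and treatment hazard ratios of 0.4 and 0.5, fill in the lower end. With no age effect (1.0), adding age changes power by at most about 0.3 points. At 1.35 the gain is about 0 to 2 points. At a treatment hazard ratio of 0.4, 40% mortality and an age hazard ratio of 2.0, power went from 66% to 75%, which matches the last row within simulation error.

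**Deaths available.** At the low end, 20% placebo mortality and a treatment hazard ratio of 0.4 give 60 × 0.20 + 60 × (1 − 0.8^0.4) = 12 + 5 = 17. At the high end, 40% in both arms gives 48. Three terms then have about 6 to 16 deaths each.

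**The case against.** The strongest reply is that nothing here is wrong. The two documents agree, the model is prespecified, and it already adjusts for a covariate that the protocol calls a good predictor of 90-day mortality. That stands.

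A reader might infer that the planned hazard ratio is biased. The documents do not support this. The imbalance is a chance event in either direction and is already part of the sampling error, and the test holds its level over all randomisations. A reader might also infer that the trial forfeits planned power. It plans none for survival: the sample size concerns MELD change, and the primary conclusion is untouched.

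The age effect is also an assumption. Being part of Lille or APACHE II does not show how much age adds beyond MELD in patients selected for MELD of at least 18 and MDF of at least 32. If it adds little, the gain is close to nil. This too stands, which is why the range starts at 1.0.

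The same reasoning could be made for albumin, which is in Lille and Child-Pugh and is not a listed MELD component. The documents do not rank the two. Age is the more natural single addition because it enters both scores described as predicting mortality, but this is a judgement.

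The objection does not show a cost that outweighs the benefit. With no age effect, the added term loses almost nothing.

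**Conclusion.** The point holds as a minor, near-free improvement to an exploratory analysis. The planned Cox model is valid, with type I error of about 5%. Adding age changes power by about 0 to 8 points over assumed age hazard ratios of 1.0 to 2.0 per SD. Gains near the top need a value close to 2.0 together with 40% mortality.

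Adding age also removes a chance shift in the hazard ratio: a factor of about 1.03 to 1.14 for a one-SE imbalance and 1.07 to 1.28 for a 1-in-20 imbalance, for age hazard ratios of 1.2 to 2.0. These sizes rest on the assumed age effect, its independence from MELD and the assumed mortality.

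It is tempting to extend the change to the five-level ordinal variable in SAP 6.13.7, whose two worst levels are deaths. No gain has been shown there, and its levels 4 and 5 depend on MELD change, for which the documents show no role for age.

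**What to change.** Before unblinding, specify the Cox model in Protocol 12.8.3 and SAP 6.13.1 with treatment, baseline MELD and age at consent (continuous, linear). Keep the MELD-only model as a sensitivity analysis. SAP 6.2 already allows a SAP amendment after the blinded data review meeting and before database lock. Leave the ordinal model in SAP 6.13.7.1 unchanged, or add age there only as an optional sensitivity analysis.

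The cost is a wording change in two documents and no new data. The hazard ratio becomes conditional on age as well as MELD, and one more parameter is estimated from about 17 to 48 expected deaths, which is tight at the lower end.

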## 12.9 Data Collection/Electronic Case Report Forms

Data will be collected using a validated electronic data capture (EDC) solution. eCRFs will be utilised for recording data from each patient meeting the eligibility criteria and being randomised in the study, and a limited amount of data will be completed for patients who fail to meet eligibility criteria (i.e. screen failures). Electronic access to the eCRF will be available to all investigator sites. All study staff responsible for entering data into the eCRF system will be trained prior to the start-up of the study. A personal log-in will be provided for all responsible personnel to allow for an audit trail relating to the study data to be maintained.

All evaluations performed shall be entered in a timely manner into the eCRF by a member of the site staff delegated responsibility for this specific task by the Principal Investigator of the clinical site. It is the responsibility of the Investigator to ensure that the eCRFs are properly completed. The data in the eCRFs should be consistent with the relevant source documents. The Investigator will sign the designated signature fields of the eCRF to confirm that the information on each screen is accurate and complete. All data must be stored in an unidentifiable form treated with strict confidentiality in accordance with applicable data-protection regulations.

Captured data will be monitored electronically and source data verification (SDV) will take place at the site where all information will be verified against the individual patient records. Any inconsistencies will be presented as queries, either as automatically generated queries if raised by the logical data checks of the eCRF system, or by manually generated queries if raised by the data validation checks or the SDV performed by the data manager (DM) or the clinical research associate (CRA), respectively. Queries shall be resolved in a timely manner by a trained member of the site staff.

## 12.10 Data Management

Data will be transmitted electronically into the web based EDC system. Data will be coded according to pre-specified dictionaries and in accordance with CRO SOPs. The handling of data, including data quality control, will comply with all applicable regulatory guidelines.

## 12.11 Protocol Deviations

Protocol deviations will be captured through site self-reporting, CRA SDV and data management edit checks, and will be recorded by the CRA throughout the study in both monitoring visit reports and in a centralised log.

## 13 REGULATORY AND ADMINISTRATIVE PROCEDURES

### 13.1 Institutional Review

Investigators will agree that the study will be conducted according to the principles of the ICH E6 Guideline on GCP and the ethical principles that have their origins in the World Medical Association Declaration of Helsinki. The Investigator will conduct all aspects of this study in accordance with all national, state and local laws or regulations.

The protocol and the PIS/ICF will be approved by the relevant competent authorities and ECs, and possibly other public bodies according to local requirements, before commencement of the study. If a protocol amendment is necessary, this will be prepared with the agreement of the national co-ordinating Investigator and signed by the relevant parties. If the amendment is considered to be substantial, it will be submitted to the competent authorities and ECs, and possibly other public bodies according to local requirements, for review and approval. The protocol amendment will not be implemented before such approvals are obtained, if required. Minor amendments which do not affect the safety or physical or mental integrity of the clinical trial participants or the scientific value of the trial (i.e. non-substantial amendments) do not need to be submitted to competent authorities

SUSAR reports and periodic safety reports will be sent to competent authorities and ECs, according to local regulations.

### 13.2 Informed Consent and Inclusion of Subjects Incapable of Providing Informed Consent

It is the responsibility of the Investigator, or a person designated by the Investigator (if acceptable to local regulation), to obtain written informed consent from each individual participating in this study after adequate explanation of the aims, methods, objectives and potential hazards of the study. If the patient is incapacitated, e.g. in the case of Grade II or Grade III hepatic encephalopathy, a relative (with the exception of certain countries) or legal representative will be responsible for giving informed consent on behalf of the patient in accordance with the Declaration of Helsinki.

Additional requirements for representatives giving informed consent for an incapacitated patient may apply in certain countries. Investigators in these countries will be notified accordingly in a protocol clarification memo and the patient information sheet and informed consent will be adapted.

Clinical trials are essential to improve the outcomes of subjects with critical illness, such as the target population of this study. However, individuals with Severe Acute Alcoholic Hepatitis comprise a critically ill patient population in which it may be difficult to obtain robust informed consent. The value and generalisability of study results is contingent upon recruitment of a representative sample of patients, ensuring that consenting participants and non-consenting participants are not systematically different. As a result, it may be necessary that persons who are incapable of giving informed consent are included in this study.

Robust measures are in place to ensure that in such situations informed consent is obtained

from an appropriate relative or legal representative. A separate ICF will be used in such cases. When a potential research subject who is deemed incapable of giving informed consent is able to give assent to decisions about participation in research, the recruiting physician must seek that assent in addition to the consent of the legally authorised representative. The potential subject's dissent must be respected.

The patient, or a relative/legal representative, if applicable, will be given the opportunity to ask questions to the investigational team. It must also be explained that they are completely free to refuse permission to enter the study or to withdraw from it at any time for any reason. Sufficient time will be given to consider participation in the study. If, after this, permission is given to enter the study, the patient, or relative/legal representative, if applicable, will be asked to sign and date one original copy of the written informed consent form (ICF). The patient, or relative/legal representative, if applicable, will then receive a copy of the signed and dated patient information sheet (PIS)/ICF. The original signed ICF will be filed in the Investigator Site File (ISF). The PIS will contain site contact information in case of any questions or medical emergency.

If, at a later stage, a previously incapacitated patient becomes able to give consent to the study, the Investigator, or delegate, must obtain informed consent from the patient for them to continue in the study.

The investigator will constantly assess the level of burden to the patients, and if new safety information results in significant changes in the risk/benefit assessment or any new information presents that may affect willingness to continue to participate, the consent form should be updated and approved, if necessary, by the Research Ethics Committee (REC)/Institutional Review Board (IRB). All patients (including those already being treated) should be informed of the new information, given a copy of the revised form and asked to give their consent to continue in the study. In the case of patients who remain unable to give consent, a relative/legal representative will receive the updated information and be asked to give consent for the patient to continue in the study. Any written information given to potential patients or relatives/legal representatives will be submitted to, and approved by, the respective Ethics Committee(s) (EC) prior to implementation.

